**Version History**

Version	Changes Made	Date Finalized
1.0	Original Version	13 September 2021

Note: From the beginning of the study in 2003, statisticians have followed the analysis plan in the Statistical Considerations section of the protocol, and this separate Primary Statistical Analysis Plan is created for submission to ClinicalTrials.gov.

## **1 Introduction**

### **1.1 Purpose**

This Primary Statistical Analysis Plan (SAP) describes the primary and key secondary outcome measures and other secondary outcome measures that will address specific study objectives of IMPAACT P1026s. The Primary SAP includes general analytic approaches for all primary outcome measures, key secondary outcome measures, and other outcome measures in the primary manuscript(s) or submitted to ClinicalTrials.gov (regardless of the reporting timeline). The Primary SAP facilitates discussion of the statistical analysis components among the lead study investigators and statisticians, helping them agree on the statistical analyses to be performed and presented in the primary analysis report.

If needed, a separate SAP will provide outlines of analyses for other objectives and outcome measures not included in the Primary SAP.

### **1.2 Version History**

Not applicable; original version.

## **2 Study Overview**

### **2.1 Overview of Study Design**

P1026s is a Phase IV, prospective pharmacokinetic (PK) study to evaluate the pharmacokinetics of selected currently prescribed antiretroviral (ARV) medicines when used alone or with tuberculosis (TB) medicines during pregnancy or with postpartum hormonal contraceptives in HIV-infected pregnant and postpartum women. The washout PK of transplacentally acquired ARV and TB drugs will be studied in the infants born to study mothers who enter the study during pregnancy. HIV-uninfected pregnant women receiving TB treatment (first line or second line) will also be enrolled to serve as a control group to evaluate the interaction between TB and ARV drugs in pregnant women.

Study Arm Groups (see arm details in Section 7 Attachment 1 and Protocol Schema):

- ARVs without TB Treatment (10 Arms)
- ARVs with First Line TB Treatment (2 Arms - one for each ARV drug)
- No ARVs with First Line Tuberculosis Treatment (1 Arm)
- Second Line TB Treatment for Drug-Resistant TB with or without ARVs (1 Arm)
- ARVs with Postpartum Contraceptives (4 Arms)

There is no randomization and stratification. Each study arm will enroll a minimum of 12 women and have a target enrollment of 25 women with evaluable 3rd trimester PK data in the ARV and TB arms, or evaluable postpartum PK data in the contraception arms. Enrollment may be restricted or adjusted so that 2nd trimester PK data are collected from at least 12 women. When combined enrollment in the increased dose darunavir arms reach 25 participants, the PK data will be evaluated to determine if the data for these arms can be combined and whether enrollment of additional participants in these arms should continue. Sample size for an ARV or TB drug arm may be increased if additional infants need to be enrolled to collect infant washout PK data. The

sample size of the second line TB drug arm may be increased above 25 to obtain additional data for less commonly used second line TB drugs.

Eligible women can enroll between 20 0/7 -37 6/7 weeks gestation or 2-12 weeks postpartum, depending on study arm. All infants of mothers enrolled during pregnancy will be enrolled in utero, after maternal enrollment. Enrolled infants who meet the requirements for washout PK sampling will undergo PK sampling. HIV-infected pregnant women without TB will be followed for 6 – 12 weeks after delivery with the exception of women on DRV/r who will be followed for 2 – 3 weeks after delivery. HIV-infected and non-infected women receiving TB treatment (first or second line) will be followed for 2 – 8 weeks after delivery. Postpartum women will be followed until 6 – 7 weeks after the initiation of hormonal contraceptives. Infants will be followed for 16 – 24 weeks of life.

Analyses for the Final Analysis Report for each study arm will be done once the last participant in that arm has completed all study visits, laboratory assays have been completed, and all queries have been resolved.

## 2.2 Hypotheses

There is no hypothesis specified in the protocol.

## 2.3 Study Objectives and Outcome Measures

This Primary SAP addresses the following primary and secondary objectives in the study protocol. Some secondary objectives were intended to be exploratory, and will be considered as “Other study objectives”. Therefore, this SAP will not include the outcome measures/analysis contents related to these exploratory objectives (see Section 2.3.2).

The study objectives below will be analyzed under an equivalence framework, including the comparisons between antepartum and postpartum PK parameters. The final analysis for each study arm will be done once the last participant for that arm has completed the last study visit and all queries have been resolved.

### 2.3.1 Primary Objectives and Outcome Measures

Arms for which the following objectives and outcome measures apply are shown in **bold**.

#### 2.3.1.1 (For arms in the ARVs without TB Treatment study arm group)

Objective:

To describe the pharmacokinetic parameters during pregnancy of selected ARV drugs currently used in the clinical care of HIV-infected pregnant women, and to compare these parameters to a) historical pharmacokinetic data from non-pregnant women and b) postpartum pharmacokinetic data from the same women in the study cohorts.

Outcome measure: a) # of women who met area under the curve (AUC) target of ARVs in 2nd trimester (2T), 3rd trimester (3T) and postpartum (PP) (see PK target in Protocol Appendix V); b) AUC, Cmax and Ctrough of ARVs in 2T, 3T and PP

**2.3.1.2 (For arms in the ARVs with First Line TB Treatment arms or No ARVs with First Line TB Treatment study arm groups)**

Objective:

To describe the pharmacokinetic parameters during pregnancy and postpartum of selected ARV drugs (efavirenz, lopinavir/ritonavir) and first line TB drugs when co-administered as part of clinical care of HIV-infected pregnant women and of first line TB drugs when used in HIV-uninfected pregnant women.

Outcome measure: a) # of women who met the AUC target for ARVs and the  $C_{max}$  target for first line TB drugs in 2T, 3T and PP (see PK targets in Protocol Appendix V); b) ARV and first line TB drug AUC,  $C_{max}$  and  $C_{trough}$  in 2T, 3T and PP

**2.3.1.3 (For arms in the Second Line TB Treatment for Drug-Resistant TB with or without ARVs study arm group)**

Objective:

To describe the pharmacokinetic parameters during pregnancy and postpartum of second line TB drugs administered as part of clinical care to HIV-infected and HIV-uninfected pregnant women.

Outcome measure: Second line TB drug AUC,  $C_{max}$  and  $C_{trough}$  in 2T, 3T and PP

**2.3.1.4 (For arms in the ARVs with Postpartum Contraceptives study arm group)**

Objective:

To describe the pharmacokinetic parameters of ARV drugs in postpartum women before and after starting hormonal contraceptives.

Outcome measure: AUC of ARVs before and after initiation of contraceptives (2-12 weeks postpartum and 6-7 weeks after contraceptive initiation, respectively).

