### 3 General Considerations

Each analysis will include all participants with evaluable data for that analysis. A participant's data will be deemed unevaluable by a protocol pharmacologist for a specific analysis if they do not have adequate pharmacokinetic evaluations to determine the pharmacokinetic exposure parameter of interest for that analysis. For safety analyses, a participant's data will be deemed unevaluable only if the participant did not receive any amount of the drug under study.

Visit windows are defined in Protocol Appendix IA-ID and Appendix II for mothers and infants, respectively. Specifically, maternal HIV RNA and CD4 tests for each PK visit allow a window of  $\pm$  8 weeks around the PK evaluation date. For mothers of non-contraceptive arms, entry visit (which may occur at the 2P or 3P visit) is the baseline; for mothers of contraceptive arms, entry visit (2-12 weeks postpartum) is the baseline. For infants, day of birth is defined as Day 0; birth visit is the baseline.

Continuous variables (e.g. gestational age) will be summarized with descriptive statistics (mean, median, standard deviation, interquartile range, and range). Categorical data (e.g. sex) will be summarized with frequencies and percentages for each category. Reports may also include listings with details related to safety events.

In this study, each arm will enroll independently. Final analysis for each arm will be done when that arm completes follow-up and PK assays have been run. Each study arm will have a separate Final Analysis Report (unless the team decides to combine analyses across certain arms).

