### 4 Analysis Approaches

For the PK related objectives, this SAP defines the descriptive PK data summaries and PK comparisons to be done by the protocol statisticians. The pharmacokinetic parameters will be calculated by the protocol pharmacologists, and their derivation/analysis will be defined in a separate Pharmacokinetic SAP.

If PK concentration values are missing due to below the level of quantification (BLQ), they will be set to  $\frac{1}{2}$  the lower limit of quantitation (LLOQ) for calculations. If an entire concentration-time profile is BLQ, the profile will be reported separately and excluded from the summary PK analysis. The comparisons to be performed to address the primary objectives for certain arms will vary according to type of drug and timing of sampling. Table 1 summarizes these comparisons for each type of drug.

Table 1: Pharmacokinetic Parameter Comparisons to be Performed for Each Type of Drug for the Primary Objectives

Type of Drug	Analysis Stage	Description of Pharmacokinetic Parameter Comparison	Type of Comparison
ARV without TB Drugs	Stage 1	Antepartum PK parameter vs. 10 th percentile from external, non-pregnant population	Between-participant
	Stage 2	Antepartum vs. postpartum PK parameters	Within-participant
ARV with First Line TB Drugs	Stage 1	Antepartum ARV PK parameter vs. 10 th percentile from non-pregnant population	Between-participant
	Stage 2	Antepartum vs. postpartum ARV PK parameters	Within-participant
	Stage 3	ARV PK parameter with TB drugs vs. ARV PK parameter without TB drugs in previous P1026s arm	Between-participant
First Line TB drugs with ARVs (HIV+) and First Line TB drugs without ARVs (HIV-)	Stage 1*	Antepartum TB drug PK parameter vs. 10 th percentile from non-pregnant population	Between-participant
	Stage 2	Antepartum vs. postpartum TB drug PK parameter, separately for HIV+ and HIV-	Within-participant**
	Stage 3	TB drug PK parameter with ARV (HIV+) vs. TB drug PK parameter without ARV (HIV-)	Between-participant
Second Line TB drugs with or without ARVs	Stage 2	Antepartum vs. postpartum TB drug PK parameters	Within-participant**
ARV with Contraceptives #	Stage 2	Postpartum ARV PK parameter before vs. after starting contraceptives	Within-participant
Contraceptives with ARVs	Stage 3	Postpartum contraceptive concentration with ARV vs. external historical controls not receiving ARV	Between-participant

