For the second line TB drugs, the PK analysis will use the Stage 2 approach described above, in which a within-participants comparison of TB drug PK exposure during pregnancy and postpartum will be performed. Note that the sample size for these comparisons may be less than the desired 25 evaluable women per drug because the inclusion criteria for this study arm only require that women are receiving at least two of the specified second line TB drugs, and because some women may complete their TB medication course before the postpartum visit where the PK sampling will be done. It may or may not be possible to perform a Stage 3 between-participants comparison of second line TB drug PK exposure in HIV-infected versus HIV-uninfected women; depending on the number of women receiving each TB drug, it may be necessary to combine data from HIV-infected and HIV-uninfected women.

For the ARV drugs being taken with postpartum contraceptives, the Stage 1 analysis above will not be performed (the Stage 1 analysis will only be done for ARV during pregnancy). A within-participants analysis similar to the Stage 2 analysis described above will be performed, except

that the ARV PK exposure parameters before versus after starting contraceptives will be compared (instead of during pregnancy versus postpartum).

For the contraceptives, a Stage 3 analysis will be performed that will compare the contraceptive concentrations observed in P1026s women receiving a protease inhibitor to data from historical controls not receiving ARVs, as reported in the available literature.

For analyses of PK secondary objectives, descriptive statistics (mean, median, standard deviation, interquartile range, and range) will be tabulated for PK outcome measures. If most infant washout PK data are below the BLQ for a given study arm, the pharmacologist may determine that the analysis report should not include an infant washout PK data summary (this will be noted in the report).

For the secondary objectives related to safety and clinical outcomes, adverse events and other safety outcome measures will be tabulated, and descriptive statistics (mean, median, standard deviation, interquartile range, and range) will be calculated for CD4 and HIV-1 RNA measurements (for HIV-infected participants only).

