#### **4.1 Statistical Tests**

Within-participant comparisons (e.g., between pregnant versus non-pregnant conditions or second versus third trimester) will be performed for continuous outcome measures using the Wilcoxon signed rank test and for dichotomous outcome measures using McNemar's test. If the statisticians determine there are not enough women with PK data available at both time points for a meaningful comparison, then no p-value will be calculated. In addition, if there are no discordant pairs for McNemar's test, then the test will not be performed. Between-participant comparisons will be performed for continuous outcome measures using the Wilcoxon rank sum test and for dichotomous outcome measures using the chi-square or Fisher exact test.

90% confidence limits for the geometric mean ratio of the PK exposure parameter in the pregnant versus non-pregnant conditions will also be calculated to describe the range of values that are consistent with the observed data and help the Protocol Team assess whether there is a clinically important difference in exposure in the two conditions. The confidence coefficient will be 90% rather than 95% to match the usual practice in the pharmacokinetic literature to show that two conditions are sufficiently similar (e.g, bioequivalence testing).

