## 5 Report Contents

Detailed descriptions of the content of each of the following sections are given in the AIP.

- 1) Maternal demographics summary
  - Race, ethnicity, and country
  - Age, gestational age, weeks after delivery and weight at PK visits
  - ARV/TB medication duration before antepartum visits; concomitant ARV/TB medications at antepartum visits
  - Viral load and CD4 at antepartum, delivery and postpartum visits
- 2) Maternal safety
  - List of AEs reported to Division of AIDS (DAIDS) as Expedited Adverse Events (EAEs)
  - List of Grade 3 or greater AEs
  - List of AEs that are possibly/probably/definitely related to study drugs, as determined by the Core Protocol Team and/or site investigators.
- 3) Maternal PK analysis (as applicable to study arm being analyzed)
  - PK descriptive summaries by parameter and study visit
  - PK parameter comparisons of antepartum vs. postpartum
  - Summary of mothers with AUC above 10th percentile in antepartum vs. postpartum
  - Summary of cord blood/maternal plasma ratio
- 4) Infant demographics
  - Birth weight, length, gestational age and most definitive HIV status
- 5) Infant safety
  - List of congenital anomalies
  - List of AEs reported to DAIDS as EAEs
  - List of Grade 3 or greater AEs
  - List of AEs that are possibly/probably/definitely related to study drugs, as determined by the Core Protocol Team and/or site investigators.
- 6) Infant PK analysis
  - Washout concentration and half-life summary

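### In the four contraceptive arms, the before/after comparison of ARV AUC cannot separate a contraceptive effect from recovery after pregnancy, and the SAP plans no look at the result by time since delivery

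*SAP*

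**What the plan says.** - **Timing.** SAP 2.3.1.4, a primary objective, sets the two ARV AUC samples at "2-12 weeks postpartum and 6-7 weeks after contraceptive initiation". Section 3 confirms that "for mothers of contraceptive arms, entry visit (2-12 weeks postpartum) is the baseline", and section 2.1 says "Postpartum women will be followed until 6 – 7 weeks after the initiation of hormonal contraceptives".
- **Comparison.** Table 1 in section 4 lists "Postpartum ARV PK parameter before vs. after starting contraceptives" as a Stage 2, within-participant comparison. The text of section 4 describes an analysis like Stage 2, except "that the ARV PK exposure parameters before versus after starting contraceptives will be compared".
- **Method.** Section 4.1 makes within-participant comparisons for "continuous outcome measures using the Wilcoxon signed rank test". It adds "90% confidence limits for the geometric mean ratio of the PK exposure parameter in the pregnant versus non-pregnant conditions"; the interval reaches the contraceptive arms because section 4 models their analysis on Stage 2. No covariate, restriction or stratification is named.
- **Comparator.** Section 2.1 lists four contraceptive arms and no randomisation. For the ARV comparison in these arms, Table 1 has no group without a contraceptive.
- **Time since delivery.** It appears only in the demographic summary of section 5: "Age, gestational age, weeks after delivery and weight at PK visits". Section 4.2 discusses one limitation, the selection of women already stable on their drugs, and not this one.

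**The concern.** A paired design removes differences between women. It does not remove anything that changes within every woman in the same direction between the two samples. Time since delivery is such a factor, because the contraceptive-free sample always comes first and is always nearer to delivery.

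The SAP itself gives reason to think this matters. Section 2.5 names lower ARV exposure in pregnancy as the main worry, and the antepartum/postpartum comparisons exist because exposure may change after delivery. Nothing in the SAP shows that the change is complete by week 2.

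If exposure is still rising at an early first sample, the after/before ratio is pushed up. A true fall caused by the contraceptive could then look like no change, or a rise could be read as an interaction that does not exist. The first error is the more troubling one here: section 2.3 places these objectives in an equivalence framework, and section 4.1 chooses 90% limits as the customary way to show similarity. Moreover, the note in 2.3.1.5 says the comparison of contraceptive levels with historical controls was not done. The ARV before/after comparison is thus the only one in Table 1 that remains for these arms.

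**Working it through.** **The plan's own figure.** There is none for this comparison: no effect size, SD, margin or power. The one calculated figure in the SAP, the exact 80% limits for 6 of 25 in section 2.5, reproduces as (0.131, 0.383) but concerns monitoring in pregnancy.

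**Step 1: order of samples.** The first sample precedes contraceptive start; the second is 6-7 weeks after it. The gap is therefore at least 6 weeks in every woman. If the contraceptive starts at the first visit, the second sample falls between 2 + 6 = 8 and 12 + 7 = 19 weeks postpartum.

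**Step 2: size, under assumed inputs.** From the SAP: first sample at week w, with w from 2 to 12; second sample at w + 6.5 (midpoint of 6-7, with the contraceptive started at the first visit). Assumed: GMR of exposure at delivery versus non-pregnant G = 0.70 or 0.80; half-time of recovery on the log scale h = 1, 2 or 3 weeks; no contraceptive effect.

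Relative exposure at week t = G^(2^(-t/h))

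Spurious ratio = G^(2^(-(w+6.5)/h)) / G^(2^(-w/h))

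Example with G = 0.70, h = 2, w = 2: first sample 0.70^0.5 = 0.837; second sample 0.70^(2^-4.25) = 0.70^0.0526 = 0.981; ratio 0.981/0.837 = 1.17.

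For first samples spread evenly from a to b weeks:

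log GMR = -ln(G) × (1 - 2^(-6.5/h)) × [h / ((b - a) ln 2)] × (2^(-a/h) - 2^(-b/h))

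Example with G = 0.70, h = 3, a = 2, b = 12: 0.357 × 0.777 × 0.433 × 0.567 = 0.068, so the GMR is 1.07.

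| First sample | Spurious after/before GMR |
|---|---|
| all at 2 weeks | 1.06-1.19 |
| all at 4 weeks | 1.01-1.12 |
| all at 6 weeks | 1.00-1.07 |
| all at 12 weeks | 1.00-1.02 |
| evenly over 2-12 weeks | 1.01-1.07 |
| evenly over 6-12 weeks | 1.00-1.04 |

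In each row the low end is G = 0.80, h = 1 and the high end is G = 0.70, h = 3.

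**Step 3: the fall that could be hidden.** A true fall of 1 - 1/ratio would show as a GMR of 1.00. Even spread: 1 - 1/1.01 = 1% to 1 - 1/1.07 = 7%. All at week 2: 1 - 1/1.06 = 6% to 1 - 1/1.19 = 16%.

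**Step 4: the test.** Signed-rank rejection was simulated with no contraceptive effect. Assumed: two-sided 0.05 (the SAP states no level), n = 25, 30% deficit at delivery, log-SD 0.2 per sample, 2,000 runs per cell.

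| First sample | h = 1 | h = 2 | h = 4 |
|---|---|---|---|
| 2-12 weeks | 5% | 11% | 27% |
| 2-4 weeks | 12% | 49% | 66% |
| 6-12 weeks | 5% | 6% | 14% |

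With n = 12 and first samples at 2-12 weeks the rates are 5-13%. Column h = 4 lies outside the range in step 2 and shows slow recovery.

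**Step 5: what a restriction would cost.** Under an even spread, first samples at 6 weeks or later keep (12 - 6)/(12 - 2) = 60% of women: 0.6 × 12 = 7 to 0.6 × 25 = 15 per arm. The standard error grows by about √(1/0.6) = 1.29.

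**Step 6: why not regress and predict at 12 weeks.** For an even spread the mean is week 7 and the variance 10²/12 = 8.33. The variance of a straight-line prediction at week 12 is (1/n)(1 + 5²/8.33) = 4/n, so its standard error is twice that of the plain mean. In simulation over the inputs of step 2 (n = 12 or 25, SD of the log ratio 0.20 or 0.28, 24 cells), its root-mean-square error was in no cell below that of the unadjusted log GMR. For G = 0.70, h = 2, n = 25, SD 0.28 it was about 0.11-0.12 against 0.07; in the closest cell both were about 0.08.

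**The case against.** **The objective is descriptive.** Section 2.3.1.4 sets out to describe, section 2.2 records no hypothesis, and section 4 says only that the values will be compared. A reader might infer that the plan attributes the whole change to the contraceptive. It does not say so. This stands and lowers the severity, but a paired GMR with a p-value, reported before versus after contraceptive start, invites that reading unless the report warns against it.

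**No input to the size comes from the documents.** Also true. Section 2.5 gives the expected direction of the pregnancy effect, but neither its size nor how fast it resolves. A reader might take the week-2 row and conclude that the plan would miss a fall of roughly 5-15%. That requires every woman to be sampled at 2 weeks; the SAP gives a 2-12 week window and no distribution within it.

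**The plan accepts early postpartum sampling elsewhere.** Women on DRV/r are followed only 2-3 weeks after delivery (section 2.1), so for that drug an early sample serves as the postpartum reference. This shows a choice by the team, not evidence that recovery is complete. The other ARV arms without TB treatment are followed for 6-12 weeks.

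**The adjustment may be planned elsewhere.** The protocol and its visit appendices, the separate pharmacokinetic SAP and the AIP were not available. The absence is verified in the SAP only.

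**It may be late to add analyses.** The SAP is dated 2021 for a study begun in 2003, and 2.3.1.5 already speaks of one comparison in the past tense. An added analysis may be post hoc and should be labelled so.

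**Conclusion.** The point holds as a limit on interpretation. On the SAP's own text, time since delivery and contraceptive use change together, in a fixed order, in every woman, and the planned analysis cannot separate them.

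If the pregnancy GMR is 0.70-0.80 and the recovery half-time 1-3 weeks, the spurious GMR is 1.01-1.07 with first samples spread evenly over the window; 1.06-1.19 is the extreme in which all are at 2 weeks. With fast recovery or late first samples the bias is negligible. The upward direction rests on pregnancy lowering exposure, which is what the SAP expects for ARVs.

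The documents do not support a stronger conclusion, that the comparison is invalid or that a confirmatory test fails: there is no confirmatory test, and the actual spread of first samples is unknown.

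**What to change.** In the SAP, for objective 2.3.1.4:

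1. Keep the unadjusted GMR with its 90% interval as the main result.
2. Beside it, report a sensitivity GMR with 90% interval for women whose first sample was at least 6 weeks postpartum.
3. Plot or tabulate log(after/before AUC) by weeks since delivery at the first sample.
4. State in section 4.2 that the comparison is confounded with time since delivery.

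Do not add a regression prediction at 12 weeks; with 12-25 women per arm it is too imprecise.

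**Cost.** SAP wording and one extra table or figure. Weeks after delivery at PK visits are already to be reported, and no visit or treatment changes. The restricted estimate rests on roughly 7-15 women per arm under an even spread and has a wider interval. It leaves some bias if recovery is slow: up to 1.04 under the step 2 inputs, and 14% false positives at a 4-week half-time. That is why it belongs beside the main result and should not replace it. If data have already been examined, label both additions as post hoc.
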